## Document History

Document	Version Date
Amendment 2	09 Dec 2024
Amendment 1	14 March 2023
Original protocol	18 Aug 2022

This amendment incorporates all revisions to date, including amendments made at the request of country health authorities and IRBs/ECs and any protocol administrative change letter(s).

## Protocol and Amendment Summary of Changes Table

### Amendment 2 (09 Dec 2024)

#### Overall Rationale for the Amendment:

The purpose of Amendment 2 is to move the secondary objectives and endpoints for PK of tafasitamab and lenalidomide, as well as immunogenicity of tafasitamab, to exploratory objectives and endpoints. Amendment is also to confirm study termination due to business decision made by Pfizer. As a result of this decision, Phase 1b will be discontinued after the last participant last visit and Phase 2 of the study will not be initiated.

Description of Change	Brief Rationale	Section # and Name
Substantial Modification(s)		
Moved the secondary objectives and endpoints for PK of tafasitamab and lenalidomide, as well as immunogenicity of tafasitamab to exploratory objectives and endpoints.	The PK of tafasitamab and lenalidomide, as well as immunogenicity of tafasitamab will not be analyzed due to the limited number of samples collected in Phase 1b and the decision to discontinue development of this drug combination across the program.	Section 1.1 Synopsis Section 3 Objectives, Endpoints, and Estimands Section 9.3.3.3 Pharmacokinetic Analyses for PF-07901801 Section 9.3.3.4 Immunogenicity Analyses for PF-07901801 Section 9.3.4 Tertiary/Exploratory Endpoint(s) Analysis

Description of Change	Brief Rationale	Section # and Name
Added statements about the study termination decision	Study to be terminated due to strategic business decision.	Section 1.1 Synopsis Section 1.2 Schema Section 2.1 Study Rationale Section 2.3.1 Risk Assessment Section 3 Objectives, Endpoints and Estimands Section 4.1 Overall Design Section 4.3.1. Dosing Regimens of PF-07901801 Section 6.3 Assignment to Study Intervention Section 9 Statistical Considerations Section 9.5 Sample Size Determination Section 10.10.2 Country-specific Requirements (Japan)
Non-Substantial Modification(s)		
Updated the EU CT number to NA; Added ClinicalTrials.gov ID	The study was not submitted to the EU and no EU participants were enrolled.	Title Page, Section 1.1 Synopsis

Description of Change	Brief Rationale	Section # and Name
Updated the text to align with the latest protocol template sections	As required by Pfizer SOP to align with the respective protocol template sections	Section 10.1.1 Regulatory and Ethical Considerations Section 10.1.4 Data Protection Section 10.1.6 Dissemination of Clinical Study Data Section 10.1.7 Data Quality Assurance Section 10.1.10. Study and Site Start and Closure Section 10.1.11 Publication Policy Section 10.1.12 Sponsor's Medically Qualified Individual
Addition of Appendix 15.	Relocated the summary of changes for prior amendments to align with the current protocol template processes.	Appendix 15: Protocol Amendment History
Clarification that blood sample for CD47 receptor occupancy will not be collected from participants in Japan. (PACL 30 Jun 2023)	This change is due to logistical challenges and limitations.	Section 1.3 Schedule of Activities: Blood sample for CD47 receptor occupancy
Clarified that blood sample for CD47 receptor occupancy will only be collected from participants in the United States and its territories. (PACL 17 Nov 2023)	This change is due to logistical challenges/limitations.	Section 1.3 Schedule of Activities: Blood sample for CD47 receptor occupancy
The following sentence was removed: "Approximately 60 minutes must elapse after the completion of PF-07901801 prior to the start of infusion of tafasitamab." (PACL 17 Nov 2023)	To provide clarity and consistency with the language that was previously updated in Section 6.1.1.1.	Section 6.1.1 Administration
Added text for Pfizer review of eligibility data. (PACL 17 Nov 2023)	To reduce risk for enrollment of non-	Section 5. Study Population

Description of Change	Brief Rationale	Section # and Name
	eligible participants, due to the complexities of the inclusion/exclusion criteria.	
Added text Fluorescence in situ hybridization (FISH) testing is required prior to enrollment if historical results are not available. (PACL 17 Nov 2023)	Clarified that if these tests were not done as part of primary diagnosis or results are not available in medical history, detection of MYC and BCL2 and/or BCL6 rearrangements should be conducted prior to enrollment to verify exclusion criteria 3 high-grade lymphoma.	Section 5.2 Exclusion Criteria, for Exclusion Criteria 3
Added text for timing of blood collection for laboratory tests, vital signs and ECGs. (PACL 06 Feb 2024)	This change is due to logistical challenges with timing of collection for laboratory tests, vital signs and ECGs	Section 8.3.2.1 Blood Pressure and Pulse Rate Section 8.3.3. Electrocardiograms
The Emergency Contact Card is being replaced by a study information card and will no longer be referenced. (PACL 02 Apr 2024)	The process for contacting a medically qualified individual has changed from a medical escalation process via a Pfizer Call Center to direct clinical team contact using a Study Team Contact List.	Table 1: Schedule of Assessments Section 10.1.12 Sponsor's Medically Qualified Individual Appendix 16: Abbreviations
Editorial and formatting changes and clarifications	For document accuracy and consistency.	Throughout the document

## 1. PROTOCOL SUMMARY

### 1.1. Synopsis

#### Protocol Title:

A Phase 1b/2 study of PF-07901801, a CD47 blocking agent, with tafasitamab and lenalidomide for participants with relapsed/refractory diffuse large B cell lymphoma not eligible for stem cell transplantation

#### Brief Title:

Phase 1b/2 study of PF-07901801, tafasitamab, and lenalidomide in transplant ineligible relapsed/refractory diffuse large B cell lymphoma participants

#### Regulatory Agency Identification Number(s):

US IND Number:	IND 135421
EU CT Number:	NA
ClinicalTrials.gov ID:	NCT05626322
Pediatric Investigational Plan Number:	Not applicable
Protocol Number:	C4971003
Phase:	1b/2

#### Rationale:

The purpose of this Phase 1b/2 study is to evaluate the safety, tolerability and potential clinical benefits of PF-07901801 in combination with standard doses of tafasitamab and lenalidomide in participants with relapsed-refractory diffuse large B cell lymphoma (R/R DLBCL) not eligible for high dose chemotherapy followed by autologous stem cell transplantation (ASCT).

A business decision was made by Pfizer to terminate the C4971003 study. The reason for study termination is not due to any safety concerns or requests from regulatory authorities. As a result of this decision, Phase 1b will be discontinued after the last participant last visit and Phase 2 of the study will not be initiated.

**Objectives, Endpoints, and Estimands:**

PHASE 1b		
Objectives	Endpoints	Estimands
Primary		
To assess dose limiting toxicity (DLTs), safety and tolerability of PF-07901801 in combination with tafasitamab and lenalidomide in adult participants with R/R DLBCL in order to select up to 2 doses of PF-07901801 for further evaluation in Phase 2 of the study.	DLTs during the DLT observation period (28 days following C1D1).	DLT rate estimated based on data from DLT-evaluable participants during the DLT observation period (28 days following C1D1).
Secondary		
To evaluate the overall safety profile of the combination.	

Adverse events (AEs) as characterized by type, frequency, severity (as graded by National Cancer Institute Common Terminology Criteria for Adverse Events [NCI CTCAE] v5.0), timing, seriousness, and relationship to study treatment.

Laboratory abnormalities as characterized by type, frequency, severity (as graded by NCI CTCAE v5.0), and timing.

	Not Applicable
To evaluate the anti-tumor activity of PF-07901801 in combination with tafasitamab and lenalidomide.	Objective response (OR), duration of response (DoR), complete response (CR), duration of complete response (DoCR), and progression-free survival (PFS) per Lugano Response Classification Criteria 2014 as assessed by the investigator.	Not applicable
To evaluate the pharmacokinetics (PK) of PF-07901801.	Pre- and post-dose concentration of PF-07901801.	Not applicable
To evaluate immunogenicity of PF-07901801.	Antidrug antibodies (ADAs) and neutralizing antibodies (Nabs) against PF-07901801.	Not applicable

PHASE 2		
Objectives	Endpoints	Estimands
Primary		
To assess the clinical anti-tumor activity of PF-07901801 in combination with tafasitamab and lenalidomide.	OR per Lugano Response Classification Criteria 2014 as assessed by the investigator.	The treatment effect of PF-07901801 in combination with tafasitamab and lenalidomide on OR per the Lugano 2014 response criteria as determined by investigator assessment from the date of first dose until the first documentation of PD, death, or start of new anticancer therapy. Participants who do not have a post-baseline disease assessment due to early PD, who receive anticancer therapies other than the study intervention prior to achieving an objective response, or who die, experience PD, or stop disease assessments for any reason prior to achieving an objective response will be counted as non-responders.
Secondary		
To assess additional efficacy outcomes of PF-07901801 in combination with tafasitamab and lenalidomide.	DoR, CR, DoCR and PFS by investigator per Lugano Response Classification Criteria 2014.	Not applicable
Select the RP3D for PF-07901801 in combination with tafasitamab and lenalidomide.	All endpoints in this study.	Not applicable
To further evaluate the overall safety profile and tolerability of PF-07901801 in combination with tafasitamab and lenalidomide.	

• AEs as characterized by type, frequency, severity (as graded by NCI CTCAE v5.0), timing, seriousness, and relationship to study treatment.

• Laboratory abnormalities as characterized by type, frequency, severity (as graded by NCI CTCAE v5.0), and timing.

	Not applicable
To evaluate the PK of PF-07901801.	Pre- and post-dose concentrations of PF-07901801.	Not applicable
To evaluate immunogenicity of PF-07901801.	ADAs and NAbs against PF-07901801.	Not applicable

## Overall Design

This is a multicenter, international, Phase 1b/2 study of different doses of PF-07901801 in combination with tafasitamab and lenalidomide in participants with R/R DLBCL who have completed at least 1 line of systemic treatment (at least 1 containing an anti-CD20 therapy), and who are not candidates for high dose therapy/ASCT.

An escalation/de-escalation approach will be used in Phase 1b to determine the PF-07901801 recommended Phase 2 dose (RP2D) (2 dose levels) in combination with tafasitamab and lenalidomide; the two dose levels will be further evaluated in Phase 2.

## Number of Participants

Approximately 70 participants will be enrolled in the study: approximately 20 participants in the Phase 1b and 50 participants in the Phase 2.

Note: "Enrolled" means a participant's, or their legally authorized representative's, agreement to participate in a clinical study following completion of the informed consent process and assignment to study intervention.

## Study Population

Adult participants ( $\geq 18$  years of age) with histologically confirmed measurable relapsed or refractory DLBCL not eligible for stem cell transplantation will be enrolled in the study.

## Key Inclusion Criteria

- Histologically confirmed DLBCL; relapsed or refractory disease.
- Participant is not a candidate for or is unwilling to undergo high dose chemotherapy and subsequent stem cell transplant or is unable to receive approved chimeric antigen receptor (CAR-T) therapy.
- Prior treatment with at least 1 line of systemic therapy (for phase 2: at least 1 and no more than 2 lines of systemic therapy). Prior therapy must include an anti-CD20 containing regimen.
- Adequate hematologic, hepatic and renal function.
- Eastern Cooperative Oncology Group (ECOG) performance status  $\leq 2$ .
- Participants are able to provide a tumor tissue sample collected before start of treatment (fresh or archival).

## Key Exclusion Criteria

- Prior treatment with an anti-CD47 or anti-CD19 (other than CAR-T) or immunomodulatory agents.

- Primary refractory DLBCL
- High-grade lymphoma (formerly known as 'double' or 'triple hit' DLBCL) or CNS lymphoma involvement.
- Prior allogeneic stem cell transplantation; autologous stem cell transplantation within 12 weeks prior to enrollment.
- Significant cardiac/cardiovascular/thromboembolic disease.
- Participants with active, uncontrolled bacterial, fungal, or viral infection.

Study Arms and Duration Study Intervention(s)			
Intervention Name	PF-07901801	Tafasitamab	Lenalidomide
Arm Name (group of participants receiving a specific treatment or no treatment)	Administered to all participants	Administered to all participants	Administered to all participants
Unit Dose Strength(s)	10 mg/mL solution for injection; 14 mL/vial	200 mg/vial	2.5 mg, 5 mg, 10 mg, 15 mg, 20 mg, 25 mg
Route of Administration	Intravenous (IV) infusion	IV infusion	By mouth (PO)
Use	Experimental	Experimental when combined with PF-07901801	Experimental when combined with PF-07901801
Investigational medicinal product (IMP) or non-IMP (NIMP)/auxiliary medicinal product (AxMP)	IMP	IMP	IMP
Dose Formulation	Single-use vials	Single-use vials	Capsules

Study Interventions Classified as NIMPs/AxMPs

Intervention Name	Fludeoxyglucose (  F) (FDG)	Paracetamol a	Diphenhydramine hydrochloride a	Cimetidine a	Methylprednisolone a
ARM Name (group of participants receiving a specific treatment)	May be administered to all participants for use with PET scan	May be administered to all participants as premedication a	May be administered to all participants as premedication a	May be administered to all participants as premedication a	May be administered to all participants as premedication a
Dose Formulation	As per SmPC	As per SmPC	As per SmPC	As per SmPC	As per SmPC
Unit Dose Strength(s)	As per SmPC	As per SmPC	As per SmPC	As per SmPC	As per SmPC
Route of Administration	IV injection	PO	PO or IV	PO	IV injection or infusion
Use	For use with PET	Premedication	Premedication	Premedication	Premedication
IMP or NIMP/AxMP	AxMP	AxMP	AxMP	AxMP	AxMP

a. Premedications that may be given as per MINJUVI SmPC [equivalent premedication(s) includes variations to the stated ones, depending on the formulations available locally and or in accordance with institutional guidelines].

## Administration

Study interventions will be administered in 28-day cycles. Lenalidomide will be administered up to C12 while PF-07901801 and tafasitamab will be administered until PD, non-tolerable toxicity, or death. PF-07901801 will be administered by intravenous (IV) infusion weekly for the first three cycles and then every two weeks for Cycle 4 and beyond. Participants will receive different dose levels as per assigned cohort.

Tafasitamab will be administered 12 mg/kg IV on Days 1, 4, 8, 15 and 22 in Cycle 1, weekly for Cycle 2 and 3 and then every 2 weeks for Cycle 4 and beyond. Lenalidomide will be administered 25 mg PO daily on Days 1 through 21 of each 28-day cycle for up to 12 cycles.

## Statistical Methods:

There is no formal hypothesis testing for the study. All analyses will be performed for the Phase 1b and Phase 2 of the study separately. All efficacy analyses and safety analyses will be performed using the Safety Analysis Set (if not otherwise specified).

### Phase 1b:

The primary endpoint of the Phase 1b of the study is the DLTs during the DLT observation period. The target number of participants per cohort is 2-4, and a minimum of 2-4 DLT-evaluable participants is required at each tested dose level of PF-07901801. Approximately 6 to 9 DLT-evaluable participants will be treated at the MTD or highest safe tested dose level for PF-07901801 before proceeding to Phase 2. The number and proportion

of participants experiencing DLTs during the DLT observation period will be summarized and listed by dose level.

**Phase 2:**

Up to 2 doses will be selected for further evaluation in Phase 2 of the study. Approximately 25 participants will be treated for each selected dose.

The primary endpoint in the Phase 2 of the study is OR per Lugano Response Classification Criteria 2014 as assessed by the investigator. OR is defined as a BOR of CR or PR according to Lugano Response Classification Criteria 2014.

ORR will be calculated along with the 2-sided 95% CI using the Wilson method.

**For both phases:**

- Secondary efficacy endpoints (OR [Phase 1b only], DoR, CR, DoCR, and PFS per Lugano Response Classification Criteria 2014 as assessed by the investigator) will be summarized by dose levels.
- Secondary safety endpoints (AEs, laboratory abnormalities):
  - AEs will be graded by the investigator according to the CTCAE v5.0 and coded using MedDRA. AE data will be reported in tables and listings and will be presented by dose levels.
  - The laboratory results will be graded according to the NCI CTCAE v5.0 severity grade and will be analyzed using summary statistics.
- Secondary PK endpoints will be analyzed and presented using descriptive summary statistics.
- Secondary immunogenicity (ADAs and Nabs): the percentage of participants with positive ADA will be summarized. Listings and summary tabulations of the ADA data at baseline and post-first dose will be generated.

**Ethical Considerations**

[figure not shown]
Patients with R/R DLBCL who are not candidates for ASCT due to age or co-morbidities have limited treatment options and poor prognosis. The combination of tafasitamab and lenalidomide has shown increased response and progression-free survival in patients with R/R DLBCL, leading to conditional approval. By engaging overlapping as well as different mechanisms with the combination of tafasitamab and lenalidomide, PF-07901801 is expected to increase anti-tumor activity in patients with R/R DLBCL. Further, available safety data of PF-07901801 as a single agent in patients with DLBCL suggest that it may be combined with other approved agents without significantly increasing their toxicity. Possible overlapping toxicity with the proposed regimens include neutropenia and thrombocytopenia; to minimize

risks, participants will be monitored frequently, including weekly blood tests for their first 8 weeks of treatment.

Therefore, taking into consideration the complementary mechanisms of action of PF-07901801 with tafasitamab and lenalidomide as well as the safety profile of PF-07901801, this combination may offer a more efficacious and tolerable treatment option for older patients or patients with co-morbidities that are not candidates for high dose chemotherapy and/or ASCT.

## 1.2. Schema

Phase 2 of the study will not be initiated per business decision made by Pfizer (protocol amendment 2).

\*A minimum of 2 to 4 participants is required at each dose level.

Approximately 6 to 9 participants will be treated at the MTD or highest safe tested dose level before proceeding to Phase 2.

### 1.3. Schedule of Activities

The SoA table provides an overview of the protocol visits and procedures. Refer to the **STUDY ASSESSMENTS AND PROCEDURES** section of the protocol for detailed information on each assessment required for compliance with the protocol.

The investigator may schedule visits or tests (unplanned visits/tests) in addition to those listed in the SoA table, in order to conduct evaluations or assessments required to protect the well-being of the participant.

**Table 1. Study Schedule of Assessment**

Visit Identifier  Abbreviations used in this table may be found in Appendix 16	Screen	On-Treatment Period (28-day Cycle)												Notes			
		Cycle 1				Cycle 2-3				≥Cycle 4				EOT	FU visits		LT FU
Cycle Day	≤28d	D1	D4	D8	D15	D22	D1	D8	D15	D22	D1	D15	7d	28d	90d	Q12W	
Visit Window		(±1d)	(±2d)	(±2d)	(±2d)	(±2d)	(±2d)	(±2d)	(±2d)	(±2d)	(±2d)	(±2d)	(±2d)	(±2d post-last TX)	(28-35d post-last TX)	(+7 post-last TX)	(±14d post 90d FU)
Informed consent	X																
Registration/randomization		X															

PFIZER CONFIDENTIAL

CT02-GSOP Oncology Clinical Protocol Template (01 April 2022)

**Table 1. Study Schedule of Assessment**

Visit Identifier	Screen	On-Treatment Period (28-day Cycle)												Notes			
		Cycle 1					Cycle 2-3				≥Cycle 4			EOT	FU visits		LTFU
Cycle Day	≤28d	D1	D4	D8	D15	D22	D1	D8	D15	D22	D1	D15	7d	28d	90d	Q12W	
 
Day relative to start of study intervention (Day 1).
 

Visit Window		(±1d)	(±2d)	(±2d)	(±2d)	(±2d)	(±2d)	(±2d)	(±2d)	(±2d)	(±2d)	(±2d)	(±2d post-last TX)	(28-35d post-last TX)	(+7 post-last TX)	(±14d post 90d FU)	
 
After 1 year of study intervention, cycle visit date windows are ±7d.
 

Disease characteristics/treatment history	X													
 
Including cancer history, disease staging (Ann Arbor), risk assessment (IPI score), prior cancer treatments, and inclusion/exclusion criteria.
 
			
Demographics/medical history	X													
 
See Section 8.1.1.
 
			
Physical examination	X	X			X		X		X		X	X					
 
A complete PE will be conducted at Screening Visit only; targeted/symptom-directed PEs will be conducted at other visits.
 
See Section 8.3.1 for additional information.
 

Body weight	X	X					X				X						
 
See Section 8.3.1 for additional information.
 
Also see Section 6.1.1 for dose calculation with weight.
 

**Table 1. Study Schedule of Assessment**

Visit Identifier	Screen	On-Treatment Period (28-day Cycle)												Notes			
		Cycle 1				Cycle 2-3				≥Cycle 4				EOT	FU visits		LTFU
Cycle Day	≤28d	D1	D4	D8	D15	D22	D1	D8	D15	D22	D1	D15	7d	28d	90d	Q12W	
 
Day relative to start of study intervention (Day 1).
 

Visit Window		(±1d)	(±2d)	(±2d)	(±2d)	(±2d)	(±2d)	(±2d)	(±2d)	(±2d)	(±2d)	(±2d)	(±2d post-last TX)	(28-35d post-last TX)	(+7 post-last TX)	(±14d post 90d FU)	
 
After 1 year of study intervention, cycle visit date windows are ±7d.
 

Vital signs	X	X	X	X	X	X	X	X	X	X	X	X	X	X			
 
On days of infusion: as per local guidelines for monoclonal antibodies, with a minimum as follows for each infusion of PF-07901801 and tafasitamab.           
 
PF-07901801: C1D1: pre (within 15 min prior), EOI (±15 min), (end of): 2h (±15 min). ≥C1D8: pre and EOI (±15 min).
 
Tafasitamab: pre, 15 (±5), 30 (±10), and then every 60 (±15) minutes during infusion and at EOI (± 20 min). After 3 infusions: pre and EOI (±15 min).
 
 
 
See Section 8.3.2 for additional information.
 

12-Lead ECG	X	X					X			X		X	X				
 
C1D1, C2D1, C3D1: Pre-PF-07901801 dose, PF-07901801 EOI (window for EOI: +30 min).
 
C4D1, C5D1, C6D1: pre PF-07901801 dose
 
See Section 8.3.3 for additional information.
 

B-symptoms	X	X					X			X		X					
 
See Section 8.3.6.
 

ECOG assessment	X																
 
Per Appendix 13.
 

PFIZER CONFIDENTIAL

CT02-GSOP Oncology Clinical Protocol Template (01 April 2022)

**Table 1. Study Schedule of Assessment**

Visit Identifier	Screen	On-Treatment Period (28-day Cycle)												Notes			
		Cycle 1					Cycle 2-3				≥Cycle 4			EOT	FU visits		LTFU
Cycle Day	<28d	D1	D4	D8	D15	D22	D1	D8	D15	D22	D1	D15	7d	28d	90d	Q12W	
 
Day relative to start of study intervention (Day 1).
 

Visit Window		(±1d)	(±2d)	(±2d)	(±2d)	(±2d)	(±2d)	(±2d)	(±2d)	(±2d)	(±2d)	(±2d)	(±2d post-last TX)	(28-35d post-last TX)	(+7 post-last TX)	(±14d post 90d FU)	
 
After 1 year of study intervention, cycle visit date windows are ±7d.
 

Diary card (lenalidomide)	X	X					X				X		X				
 
See Section 6.5.
 
To be collected through Cycle 12 or EOT, whichever occurs first.
 

AEs/SAEs	Continuously active collection																
 
See Section 8.4 for additional information.
 

Medications	Concomitant medications												Subsequent anticancer therapy(ies)				
 
Concomitant medications to be collected continuously from the time of ICD through EOT.
 

CD19 expression (if post CAR-T)	X																
 
CD19 expression to be measured in participants with prior CAR-T treatment: local lab test (if available) and tissue for future central testing (both must be a sample after CAR-T and prior to C1D1).
 
See also Section 8.7.8.
 

Survival status														X	X		
 
May be conducted by phone.
 

Local Laboratory Assessments																	
 
See Section 8.3.4 for additional information.
 
See Appendix 2 for a list of clinical laboratory tests to be done.
 

PFIZER CONFIDENTIAL

CT02-GSOP Oncology Clinical Protocol Template (01 April 2022)

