## **6.9. Prior and Concomitant Therapy**

Hormonal contraceptives that meet the requirements of this study are allowed to be used in participants who are WOCBP (see [Appendix 4](#)).

Concomitant treatment considered necessary for the participant's well-being may be given at discretion of the treating physician.

See [Section 6.9.4](#) regarding limitations on prophylactic use of colony stimulating factors or erythropoiesis-stimulating agents during the DLT period.

All concomitant treatments, blood products, as well as nondrug interventions received by participants from screening until the EOT visit will be recorded on the CRF.

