### **8.1.2. Follow-Up Visits and LTFU**

At least 28 calendar days, and no more than 35 calendar days after discontinuation of study intervention, participants will return to undergo review of concomitant treatments, vital signs,

PFIZER CONFIDENTIAL

CT02-GSOP Oncology Clinical Protocol Template (01 April 2022)

Page 88

and assessment for resolution of any treatment related AEs. Participants continuing to experience AEs at this point following discontinuation of treatment will continue to be followed at least every 4 weeks until resolution or determination, in the clinical judgment of the investigator, that no further improvement is expected.

If the unresolved AE is considered by the investigator as possibly related to or associated with ADA formation, the participant may be asked to return for ADA blood sampling at up to 3 month intervals (if feasible given the underlying disease), until the AE or its sequelae resolve or stabilize at a level acceptable to the investigator and sponsor up to a maximum of 9 months from the last study treatment.

The 90-day post-dose follow-up visit for AEs, contraception check, and subsequent anticancer therapy(ies) may be performed via remote contact (eg, telephone). The investigator may complete these follow-up visits in clinic if any concerns are noted during the remote contact.

Participants discontinued from study interventions before disease progression will enter the LTFU phase and be contacted until disease progression, the start of a new anti-cancer therapy or death, whichever comes first. Participants will be contacted by telephone every 12 weeks from the 90-day follow-up visit (24 weeks from the last dose) to confirm survival status and to collect any new anti-cancer therapies. Onsite visits may be required to conduct follow-up assessments described in the [SoA](#) (Section 1.3), including scans.

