#### Assessment of Causality

- The investigator is obligated to assess the relationship between study intervention and each occurrence of each AE or SAE. The investigator will use clinical judgment to determine the relationship.
- A "reasonable possibility" of a relationship conveys that there are facts, evidence, and/or arguments to suggest a causal relationship, rather than a relationship cannot be ruled out.
- Alternative causes, such as underlying disease(s), concomitant therapy, and other risk factors, as well as the temporal relationship of the event to study intervention administration, will be considered and investigated.

- The investigator will also consult the IB and/or product information, for marketed products, in their assessment.
- For each AE or SAE, the investigator **must** document in the medical notes that they have reviewed the AE or SAE and have provided an assessment of causality.
- There may be situations in which an SAE has occurred and the investigator has minimal information to include in the initial report to the sponsor. However, it is very important that the investigator always make an assessment of causality for every event before the initial transmission of the SAE data to the sponsor.
- The investigator may change his/her opinion of causality in light of follow-up information and send an SAE follow-up report with the updated causality assessment.
- The causality assessment is one of the criteria used when determining regulatory reporting requirements.
- If the investigator does not know whether or not the study intervention caused the event, then the event will be handled as “related to study intervention” for reporting purposes, as defined by the sponsor. In addition, if the investigator determines that an SAE is associated with study procedures, the investigator must record this causal relationship in the source documents and CRF, and report such an assessment in the dedicated section of the CT SAE Report Form and in accordance with the SAE reporting requirements.

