6.6.4. Concomitant Medications and Nondrug Treatments

The following analyses will be based on the Safety Analysis Set.

Concomitant medications are medications, other than study medications, which started prior to first dose date of study treatment and continued on on-treatment period as well as those started during the on-treatment period. Prior medications are medications, other than study medications and pre-medications for study drug, which are started before the first dose of study treatment.

Prior and concomitant medications will be summarized from the 'Concomitant Medications' eCRF page. Pre-medications for study drug will also be summarized separately.

Summary of prior and concomitant medications will include the number and percentage of patients by Anatomical Therapeutic Chemical (ATC) Classification level 2 and preferred term. A patient will be counted only once within a given drug class and within a given drug name, even if he/she received the same medication at different times. If any prior or concomitant medication is classified into multiple ATC classes, the medication will be summarized separately under each of these ATC classes. The summary tables will be sorted on decreasing frequency of drug class and decreasing frequency of drug name in a given drug

class. In case of equal frequency regarding drug class (respectively drug name), alphabetical order will be used. In case any specific medication does not have ATC classification level 2 coded term, it will be summarized under 'Unavailable ATC classification' category.

A listing of concomitant medications will be created with the relevant information collected on the 'Concomitant Medications' eCRF page.

A listing of concurrent procedures will be created with the relevant information collected on the 'Non-drug Treatments' eCRF page.

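### CRF recording of concomitant medications ends at the EOT visit (Day 5-9 after last treatment), but the SAP tabulates them to last dose + 28 days, so new starts in the last 19-23 days of that window will be absent from the table

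*Protocol*

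**What the plan says.** **Collection.** The Medications row of the schedule of activities (Protocol 1.3, Table 1) carries the note "Concomitant medications to be collected continuously from the time of ICD through EOT". After EOT, the row shows only subsequent anticancer therapy. Protocol 6.9 sets the same limit separately: concomitant treatments, blood products and non-drug interventions "received by participants from screening until the EOT visit will be recorded on the CRF". The EOT column is set at 7 days, with a plus-or-minus window of "2d post-last TX".

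**Later review.** Protocol 8.1.2 has a follow-up visit at least 28 and "no more than 35 calendar days after discontinuation of study intervention, participants will return to undergo review of concomitant treatments", together with vital signs and AE resolution. It does not say whether that review is entered on the CRF.

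**Analysis.** SAP 6.6.4 defines concomitant medications as those begun before first dose that "continued on on-treatment period as well as those started during the on-treatment period". The summary is taken from the Concomitant Medications eCRF page. SAP 5.2.7 ends the on-treatment period at last dose plus 28 days, or on the day before new anticancer drug therapy starts, whichever is earlier. SAP 6.7.1 uses the same period for treatment-emergent AEs.

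**Related provisions.** Protocol 8.4.1 actively collects AEs to at least 28 days after PF-07901801 or lenalidomide, or to 90 days after tafasitamab, whichever is longer. Protocol 8.4.3 requires relevant concomitant medications to be supplied as follow-up information on an AE or SAE.

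**The concern.** The period that the SAP tabulates is longer than the period for which the protocol asks sites to fill in the page behind the table. SAP 2.1 lists no departure from the protocol, so nothing tells the reader of the study report about the difference.

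What is at stake is whether a descriptive safety table means what its definition says. The AE tables and the medication table will share the on-treatment label, but only the AE tables will cover the whole post-dose window. Growth factors, transfusions or anti-infectives first given between EOT and Day 28 would have no required entry on the CRF. Neutropenia, thrombocytopenia and infections are among the risks named in Protocol 2.3.1. A reader comparing the frequency of such events with the frequency of their treatment would see a shortfall that comes from the collection rule.

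**Working it through.** The plan gives no figure of its own here, so the check is day arithmetic on the windows, counted from last dose of study treatment.

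**Inputs**
- EOT visit: Day 7 ± 2, so Day 5 to Day 9 (Protocol Table 1).
- End of CRF recording of concomitant treatments: the EOT visit (Protocol Table 1 note and 6.9).
- End of the SAP on-treatment period: Day 28, if no new anticancer drug therapy starts earlier (SAP 5.2.7).
- Follow-up visit: Day 28 to Day 35 (Protocol 8.1.2).
- End of active AE collection when tafasitamab governs: Day 90 (Protocol 8.4.1).

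**Uncollected part of the SAP window** = 28 − EOT day

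| EOT visit | Days not collected | Share of the 28 post-dose days |
|---|---|---|
| Day 5 | 28 − 5 = 23 | 23/28 = 82% |
| Day 7 (nominal) | 28 − 7 = 21 | 21/28 = 75% |
| Day 9 | 28 − 9 = 19 | 19/28 = 68% |

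**Share of the whole on-treatment period.** SAP 6.6.4 summarises from first dose, so the share of the full window is smaller. Assume dosing to the last scheduled day and EOT on Day 7.
- One cycle: last infusion on Day 22, window 22 + 28 = 50 days; 21/50 = 42%.
- Six cycles: last lenalidomide on Day 5 × 28 + 21 = 161, window 161 + 28 = 189 days; 21/189 = 11%.
- Twelve cycles: last lenalidomide on Day 11 × 28 + 21 = 329, window 329 + 28 = 357 days; 21/357 = 6%.

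**What is lost inside the gap.** A medication begun before EOT and still running is already on the page. Only new starts between EOT and Day 28 are lost.

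**Whether the existing visit would close the gap.** The follow-up visit is never before Day 28, so a CRF review there reaches the end of the SAP window. Starts on Days 29 to 35 fall outside the on-treatment period, and the existing SAP definition would not count them.

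**Against AE collection.** When tafasitamab governs, AEs are collected for 90 − 7 = 83 days beyond EOT (81 to 85 over the visit window). The SAP medication table does not run that far, so this is context and not part of the size of the mismatch.

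**The case against.** The strongest reply is that the EOT cut-off looks deliberate. It is stated twice, and the schedule then switches to subsequent anticancer therapy, which is the post-EOT treatment that efficacy censoring needs. The table is descriptive, and no DLT, response, DoR or PFS analysis draws on it. Phase 2 will not start, so the plan leaves approximately 20 Phase 1b participants. All of this stands, and it limits the weight of the point. It does not make the SAP table match its own definition.

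Protocol 8.1.2 also does not contradict 6.9. The protocol often separates what is checked in source from what is entered on the CRF, and a review kept in source is compatible with both sections. That is correct. The firm mismatch is between the protocol's recording rule and the SAP.

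Three stronger readings are tempting, and the documents do not support them:
- *All treatment for AEs after EOT is missing.* Protocol 8.4.3 requires medications relevant to an event to be supplied as follow-up information. What is missing is entries on one CRF page and the table built from it.
- *Cause and severity of late AEs cannot be judged.* Protocol 10.3.3 does ask the investigator to weigh "Alternative causes, such as underlying disease(s), concomitant therapy, and other risk factors", but this is done by clinical judgment and documented in the medical notes. The CTCAE grade is likewise assigned by the investigator. The SAP derives neither from the medication page.
- *Cytopenias and infections delayed until after stopping are the expected toxicities.* The protocol names these risks but does not say that they typically appear after treatment ends. For PF-07901801, Protocol 2.2.3.1 describes platelet falls mostly on dosing days, with recovery to baseline.

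**Conclusion.** The mismatch is real and minor. As written, medications newly started in about the last 21 days (19 to 23) of the SAP on-treatment window will be absent from the concomitant-medication summary, while treatment-emergent AEs are tabulated over the full window.

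This assumes that sites follow the schedule note and 6.9 as written, that the EOT visit is held within its window, and that no new anticancer drug therapy starts before Day 28. If such therapy does start, the SAP window closes sooner and the gap shrinks. How many medications would be lost cannot be estimated from the documents. No primary or efficacy result is affected.

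The study's termination does not remove the point. Phase 1b runs to the last participant's last visit, and its safety tables remain to be reported.

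**What to change.** In the schedule note and Protocol 6.9, replace the EOT cut-off with the 28-35 day follow-up visit for CRF recording of concomitant drugs, blood products and non-drug interventions. Collection then matches both the SAP on-treatment period and the review in Protocol 8.1.2. SAP 6.6.4 needs no change. The cost is two wording changes and about three more weeks of entries on an open CRF page, made at a visit that already exists. Recording to the end of active AE collection is not needed for this table.

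For participants whose collection can no longer be extended, amend SAP 6.6.4 so that the summary covers medications through the EOT visit, and state that limit in the table title or footnote. That costs one line and no new data. The table would then be accurately labelled but would still stop about three weeks short of the AE tables.
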